Very limited background information is available in the literature for the incidence rates of acute pancreatitis, pancreatic cancer and thyroid cancer, in particular medullary thyroid cancer in adult type 2 diabetes patients treated with GLP-1 agonists (i.e., exenatide and liraglutide) and other anti-diabetics. Therefore, the data from such a study will help contextualize these events expected to be observed in the patient registry of lixisenatide.

II.8. Research Question and Objectives

A series of cohort studies will be conducted based on prescription databases in Denmark, Norway, and Sweden, with a view to country-specific analysis and a planned meta-analysis of the three studies.

The primary objectives of this study are to estimate:

- 1. Incidence rates of acute pancreatitis (ICD10 K85) among adult type 2 diabetes patients treated with GLP-1 receptor agonists (i.e. exenatide and liraglutide), as well as patients treated with other anti-diabetic drugs and to examine the risk of acute pancreatitis in users of GLP-1 receptor agonists compared to users of other anti-diabetic medications;
- 2. Incidence rates of pancreatic cancer (ICD10 C25) among adult type 2 diabetes patients treated with GLP-1 receptor agonists (i.e. exenatide and liraglutide), as well as patients treated with other anti-diabetic drugs and to examine the risk of pancreatic cancer in users of GLP-1 receptor agonists compared to users of other anti-diabetic medications;
- 3. Incidence rates of thyroid cancer (ICD10 C73) (especially medullary thyroid cancer) among adult type 2 diabetes patients treated with GLP-1 receptor agonists (i.e. exenatide and liraglutide), as well as patients treated with other anti-diabetic drugs and to examine the odds ratio of medullary thyroid cancer in users of GLP-1 receptor agonists compared to users of other anti-diabetic medications.

This study is designed to focus on the risk associated with use of GLP-1 agonists and will investigate the following primary hypotheses:

- 1. That adult patients prescribed GLP-1 RAs have an increased risk of acute pancreatitis when compared to patients prescribed other types of anti-diabetic drugs;
- 2. That adult patients prescribed GLP-1 RAs have an increased risk of pancreatic cancer when compared to patients prescribed other types of anti-diabetic drugs;

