A potentially major issue surrounds the well-documented under-diagnosis of pancreatic cancer in some Cancer Registries. Kilander et al (2012) recently examined this situation in the Swedish Cancer Registry. From a total of 31,067 cases of pancreatic cancer, 44% were registered in the Hospital Patient Discharge Register but not in the Cancer Registry indicating an overwhelming under-reporting of pancreatic cancer in the Cancer Registry. Thus, diagnoses of pancreatic cancer will be sought in both the Cancer Registry and the Hospital Patient Discharge Registry in each of the countries.

Covariates

The key variables in the study will be obtained from the prescription databases (age, gender, insulin and other diabetes medications and other prescriptions); the hospital discharge registries (date of diagnosis, gallstones and obstruction of the pancreatic duct); the cancer registries (date of diagnosis, cancer site, histology and outcome of cancer); and the national death registers (date and cause of death).

All analyses will be stratified by age and gender and in addition by treatment history.

In order to improve the analysis all efforts will be made to collect additional information on several other potential confounding variables.

Potential confounders for pancreas cancer will include smoking history, alcohol intake, family history of pancreas cancer, a previous diagnosis of Multiple Endocrine Neoplasia (especially MEN1) and chronic pancreatitis.

Potential confounders for acute pancreatitis will include duration of diabetes, presence of gallstones, prior use of anti-diabetic medications, alcohol intake and obstruction of the pancreatic duct.

Potential confounders for thyroid cancer will include duration of diabetes, prior use of anti-diabetics, radiation treatment to the head and neck, iodine intake, hormonal and reproductive treatment, history of goiter or benign thyroid nodules, history of cancer, diagnosis of Multiple Endocrine Neoplasia type 2 (MEN2), and family history of medullary thyroid cancer at the baseline.

The availability of these additional data will differ between the individual countries. A dictionary of compatible covariate information will be compiled at the outset of the study to enable information common to more than one study to be collected and recorded in a manner that will enable the data to be used across studies.

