Data analysis Descriptive analysis will be performed and total follow-up time for lixisenatide users will be calculated. For pancreatitis, pancreatic cancer and thyroid cancer, the expected number of cases will be estimated annually after launch using the background rates obtained from the retrospective databases study. If the observed number of cases for the events of interest, respectively, is significantly higher than the expected number of cases, further investigation may be warranted following discussion with the regulatory authorities.

Milestones The registry will be initiated after the launch of lixisenatide and preparations will begin with immediate effect to ensure that the systems are in place prior to launch. Status reports will be submitted to the Agency annually, together with the RMP update as planned. Final report will be submitted to the Agency at the end of the registry.

III.5 Amendments and Updates

This is the initial protocol and any amendments will be placed here in a timely manner.

III.6 Milestones (events in months)

The registry will be initiated after the launch of lixisenatide and preparations will begin with immediate effect to ensure that the systems are in place prior to launch. Status reports will be submitted to the Agency annually, together with the RMP update as planned. Final report will be submitted to the Agency at the end of the registry.

However, if a sufficient number of participants are captured for any outcome(s) of interest earlier before the end of registry, the final data analysis for the particular outcome(s) will be started immediately and the study report will be made available within 12 months.

Start of preparatory	Т0	Development of draft Protocol	
phase	T0+1	Meeting with Sanofi Global Pharmacovigilan	
		and Epidemiology, Regulatory, and Medical	
		Affairs	
	T0+1	Establishment of Scientific and Steering	
		Committee	
	T0+2	Meeting of local Principal Investigators to refine protocol	
	T0+3	Protocol agreed and submitted to CHMP EMA	
	T0+6	Development of data collection module	
	T0+7	Synthesis of background information on	
		disease rates in populations	
	T0+8	Preliminary Pilot Testing of data collection and	
		data transfer	
	T0+9	Final agreement on Protocol from CHMP	
	T0+9	IRB/Ethics Approval	
	T0+10	Registry ready to launch	
Start of data collection	Date of mark	ket authorization for Lixisenatide – T	
End of data collection	2018		
Study progress reports	Yearly		
Interim reports	Yearly		

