- Romley et al (2012) conducted a study of exenatide therapy and the risk of pancreatitis and pancreatic cancer in a privately insured population. This is a retrospective cohort study on type 2 DM patients with employer provided health insurance from 2007 to 2009. Among the 268,561 patients included in the study, only 2.6% used exenatide. The hospitalization rate for acute pancreatitis among patients who used at least one exenatide prescription was 1.96 per 1000 patients compared to 2.49 per 1000 patients who never used exenatide (p-value = 0.167).
- MacConell et al (2012) examined the safety and tolerability of exenatide twice daily in patients with type 2 diabetes with an integrated analysis of 5594 patients from 19 placebo-controlled and comparator-controlled clinical trials This is an integrated analysis of 19 RCT carried out by the manufacturer. The incidence rates for pancreatitis were not statistically different between groups.
- Elashoff et al (2011) reported on the disproportion of the FDA-AERS database of reported adverse events showed an increased risk of acute pancreatitis with exenatide: OR = 10.68 (p-value vs control drugs=2 x 10e-16). However, this must be interpreted bearing in mind the known limitations of this database (e.g. http://www.ncbi.nlm.nih.gov/pubmed/15317031).

The literature can be summarised by observing that the small number of reported events and other design limitations of the studies currently available does not allow for clear conclusions to be drawn, one way or another, at the present time.

Pancreatic Cancer

Besides observing a high number of pancreatitis cases, Elashoff et al (2011) also reported on pancreatic cancer in patients treated with exenatide $[OR=2.95 (p \text{ value vs control drugs}=9 \times 10e-5)]$). There are no further clinical studies that address this issue. Experimental data show that GLP-1 agonists increase beta-cell mass in rodents, But human trials do not support the rodent data (Brubaker et al, 2009)..

Thyroid Cancer

The rodent calcitonin producing C-cell expresses GLP-1Rs, and sustained GLP-1R activation results in increased calcitonin secretion, C-cell hyperplasia and medullary thyroid cancer, predominantly in rats. In contrast, C cells within the monkey and human thyroid gland exhibit lower levels of GLP-1R expression, and prolonged administration of liraglutide at very high doses does not produce C-cell proliferation in monkeys (Drucker et al, 2011; Bjerre Knudsen et al, 2010).

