A review on the association between glucagon-like peptide-1 receptor agonists and thyroid cancer (Chiu et al., 2012) concludes that GLP-1 agonists might increase the risk of thyroid C-cell pathology in rodents, but its risk in humans awaits confirmation.

Therefore, the effects of GLP-1 on human cancer development are overall unknown and difficult to be extrapolated from pre-clinical studies. In addition, the small number of cases and the lack of biological plausibility raise doubts between the use of GLP-1 agonists and the occurrence of cancer (pancreatic, thyroid or overall). Therefore longer-term, better designed epidemiological studies are required, in order to assess any risks associated with GLP-1 RA use.

Design of Investigative Study

Two studies have been prepared and the patient registry is presented below. The rationale behind both studies revolves chiefly around the concept of performing the Registry study in the same populations where the incidence rates of acute pancreatitis, pancreatic cancer and thyroid cancer, in particular medullary thyroid cancer in adult patients with type 2 diabetes treated with GLP-1 agonists (i.e., exenatide and liraglutide) and other anti-diabetics are established.

Very limited background information is available in the literature for the incidence rates of acute pancreatitis, pancreatic cancer and (medullary) thyroid cancer in adult type 2 diabetes patients treated with GLP-1 agonists (i.e., exenatide and liraglutide) and other anti-diabetics. Therefore, the data from such a study will help contextualize these events expected to be observed in the patient registry of lixisenatide.

"On 15 November 2012, the Committee for Medicinal Products for Human Use (CHMP) adopted a positive opinion, recommending the granting of a marketing authorisation for the medicinal product Lyxumia. The active substance of Lyxumia is lixisenatide, a glucagon-like-peptide-1 (GLP-1) analogue medicinal product. Like native GLP-1, lixisenatide stimulates insulin release from the pancreatic islets, suppresses glucagon secretion, delays gastric emptying and reduces body weight. A pharmacovigilance plan for Lyxumia will be implemented as part of the marketing authorisation." (from EMA - Lyxumia).

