The pharmacovigilance plan includes setting up a patient registry of type 2 diabetic patients taking lixisenatide. This would represent a proactive risk assessment in the post approval setting that allows for prospective follow-up and monitoring of occurrences of any of the outcomes of interest, i.e. pancreatitis, pancreatic cancer and thyroid cancer (especially medullary carcinoma of the thyroid).

The registry population will be representative of the population actually using the product since it should include all patients regardless of age, comorbidities or concurrent treatments. Follow up duration will be long enough to encompass delayed risks, consequences of long term use and effects of various combinations and alternations of treatments if any.

III.8 Research Question and Objectives

Study objectives

In the context of pharmacovigilance activity of the EU RMP (European Union Risk Management Plan), it has been agreed with the European Medicines Agency (EMA) to develop a Patient Registry of patients with diabetes exposed to lixisenatide.

The primary objectives of this study are to monitor the occurrences of:

- 1. acute pancreatitis,
- 2. pancreatic cancer
- 3. thyroid cancer, especially medullary carcinoma of the thyroid,

among adult type 2 diabetes patients treated with lixisenatide and to compare their risks with that of users of (1) other GLP-1 receptor agonists from the Database Study ; (2) other diabetic medications from the Database Study; and (3) the general population. The assembled cohort will be constantly monitored for these events to detect and emerging signal as quickly as possible.

Declaration of Study Hypotheses

This study is designed to focus on the risk associated with use of lixisenatide and will investigate the following primary hypotheses:

- 1. That adult patients prescribed lixisenatide have an increased risk of acute pancreatitis when compared to the expected risk calculated for the other GLP-1 RA users;
- That adult patients prescribed lixisenatide have an increased risk of pancreatic cancer when compared to the expected risk calculated for the other GLP-1 RA users;
- 3. That adult patients prescribed lixisenatide have an increased risk of thyroid cancer (especially medullary carcinoma of the thyroid) when compared to the expected risk calculated for the other GLP-1 RA users;

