Comparison of the incidence of these three conditions among users of lixisenatide and users of other GLP-1 receptor agonists will be available from the companion study among databases. This will provide an important background when interpreting any Odds Ratio found.

- 4. That adult patients prescribed lixisenatide have an increased risk of pancreatitis when compared to the expected risk calculated for other diabetic medications (which will also be divided into groups of oral medications (an indicator of less severe diabetes) and insulin (an indicator of more severe diabetes);
- That adult patients prescribed lixisenatide have an increased risk of pancreatic cancer when compared to the expected risk calculated for other diabetic medications (which will also be divided into groups of oral medications (an indicator of less severe diabetes) and insulin (an indicator of more severe diabetes);
- 6. That adult patients prescribed lixisenatide have an increased risk of thyroid cancer (especially medullary carcinoma of the thyroid) when compared to the expected risk calculated for other diabetic medications (which will also be divided into groups of oral medications (an indicator of less severe diabetes) and insulin (an indicator of more severe diabetes);

What is requested is to monitor the occurrence of pancreatitis, pancreas cancer and thyroid cancer in patients with diabetes receiving lixisenatide and to identify any potential signal indicating an increased level of pancreatitis, pancreas cancer and thyroid cancer as reliably and as quickly as possible. Comparisons need to be made with the background rate in patients with diabetes and also the general population before conclusions can be drawn. [Patients with diabetes have a background increased risk of both pancreatitis and pancreas cancer].

The comparison between risk of outcome events with different treatments will require to be handled very carefully. The only way to make such comparisons in an unbiased manner would be via a randomised clinical trial. In the observational studies proposed herein there are other factors, such as patient characteristics and physician choice, which may influence treatment choice. The products in question will not be distributed to patients in a randomised manner.

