² An external blinded committee (Pancreatic Safety Assessment Committee or PSAC) has been appointed to review all pancreatic adverse events occurring in clinical trials of lixisenatide. The PSAC Charter has not been finalized, yet. However, the criteria for adjudication of acute pancreatitis will be adapted from those proposed by Banks, Freeman, and the Practice Parameters Committee of the American College of Gastroenterology (Am J. of Gastroenterology 2006;101:2379-2400) and Frossard et al. (Lancet 2008;371:143-52.).

Similarly to the Database Study, each national centre will be responsible for the data storage and data management of the individual-level data, following all national and European directives regarding the well being and rights of each study subject. Each centre has an excellent track record of successfully undertaking similar research respecting all moral and legal requirements.

Only de-identified data will be stored at IPRI, and this will be done in a secure manner: data will password protected, and stored on local machines.

III.9.7 Data Analysis

Descriptive analysis will be performed and total follow-up time for lixisenatide users will be calculated.

Figure II.9.7.3: General study overview

For acute pancreatitis, pancreatic cancer and thyroid cancer, the expected number of cases will be estimated annually after launch using the background rates obtained from the retrospective databases study.

If the observed number of cases for the events of interest, respectively, is significantly higher than the expected number of cases, further investigation may be warranted following discussion with the regulatory authorities.

An independent **Scientific Steering Committee** will be appointed to oversee the study and advise on treatment, methodological and biostatistical issues. This group will meet regularly throughout the duration of the study and incorporate a **Biostatistical Advisory Group**, to advise on all aspects of the design and data analysis.

The Scientific Steering Committee will comprise:

[name] University of Perugia Perugia, Italy

[name] University College London London, United Kingdom

[name] Robertson centre for Biostatistics University of Glasgow, Glasgow, United Kingdom

[name] Department of Biostatistics Yale University School of Public Health New Haven, United States of America

[name] McMaster University, Hamilton, Canada

[name] Mount Sinai Hospital New York, United States of America.

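### The Registry's observed/expected trigger is stated only for thyroid cancer as a whole, so an excess of the medullary carcinoma its hypotheses emphasise is diluted

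*Protocol*

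**What the plan says.** Section III.8 (Research Question and Objectives) makes thyroid cancer a primary Registry outcome with medullary carcinoma picked out. Hypothesis 3 speaks of an "increased risk of thyroid cancer (especially medullary carcinoma of the thyroid) when compared to the expected risk calculated for the other GLP-1 RA users". Hypothesis 6 repeats this against a different comparator: "increased risk of thyroid cancer (especially medullary carcinoma of the thyroid) when compared to the expected risk calculated for other diabetic medications". The Registry's outcome coding in III.9.4 again places the medullary emphasis within C73. The thyroid mechanism described in III.7 concerns C-cells: "sustained GLP-1R activation results in increased calcitonin secretion, C-cell hyperplasia and medullary thyroid cancer, predominantly in rats".

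The analysis is set one level up. III.9.7 reads: "For acute pancreatitis, pancreatic cancer and thyroid cancer, the expected number of cases will be estimated annually after launch". The Registry synopsis says the same: "For pancreatitis, pancreatic cancer and thyroid cancer, the expected number of cases will be estimated annually after launch using the background rates". In both places, an observed count significantly above the expected one may prompt further investigation after discussion with regulators. Table III.9.5.2 uses a single thyroid rate, 6.13 per 100,000 person-years, for all types.

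The Database Study, which supplies the background rates, keeps the medullary emphasis: "Incidence rates of thyroid cancer (ICD10 C73) (especially medullary thyroid cancer) among adult type 2 diabetes patients". Section II.9.4 notes that tumour type can be read from the morphology code, and III.9.4 adopts those data sources for the Registry.

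**The concern.** The observed/expected comparison is the Registry's stated route from data to regulatory action. If medullary carcinoma is a small part of thyroid cancer, even a large relative excess moves the all-thyroid ratio only modestly. A non-significant thyroid ratio could then be read as reassurance about a tumour on which it carries little information. The protocol asks for signals to be found reliably and quickly, and pooling a rare subtype with its parent site works against that when the subtype is the one under suspicion.

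**Working it through.** **Inputs from the protocol.** Prevalent diabetes 1,049,810 and 55,000 new cases a year (III.9.5); five-year person-years = 5 × p × 1,049,810 + 10 × p × 55,000 for exposure p; all-thyroid rate 6.13 per 100,000; Poisson model; significance level 0.05. Sidedness is not stated. I use one-sided, since the hypotheses and the rule concern increases.

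**Assumption from outside the documents.** Medullary share s of expected thyroid cases: 2%, 5% and 10%.

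**The plan's own figure.** At p = 5%, person-years = 289,952.5 and expected cases = 289,952.5 × 0.0000613 = 17.8, as printed. The critical count k is the smallest with P(X ≥ k | E) ≤ 0.05. At E = 17.8, k = 26, and power for a ratio of 2 is P(X ≥ 26 | 35.5) = 0.96. The printed 92% is the value at E = 15 (k = 23, power 0.919), which fits a look-up in a table with rounded E. The printed figure is therefore reproduced and slightly conservative.

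**Dilution.** All-thyroid ratio = 1 + s(R − 1). For R = 10: 1.18, 1.45 and 1.90 at s = 2%, 5% and 10%. For R = 5: 1.08, 1.20 and 1.40.

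**Power.** All-thyroid: critical count from E, mean E × (1 + s(R − 1)). Medullary only: critical count from sE, mean RsE.

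Tenfold excess, all-thyroid v medullary count:

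| Exposure | E (all) | k (all) | s = 2% | s = 5% | s = 10% |
|---|---|---|---|---|---|
| 1% | 3.55 | 8 | 6% v 16% | 15% v 53% | 37% v 69% |
| 2% | 7.11 | 13 | 8% v 42% | 24% v 69% | 59% v 97% |
| 5% | 17.77 | 26 | 16% v 69% | 51% v 98% | 93% v 100% |
| 10% | 35.55 | 47 | 24% v 97% | 76% v 100% | 99.6% v 100% |

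The medullary critical counts are 2/2/3, 2/3/3, 3/4/5 and 3/5/8 down the rows.

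Fivefold excess at 5% exposure: 8% v 26%, 18% v 65% and 44% v 94%.

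Doubling, s = 2/5/10%: 3.2/3.7/4.6% v 0.9/5.0/3.5% at 1% exposure; 3.4/4.1/5.6% v 3.4/3.5/17.2% at 2%; 4.8/6.2/9.3% v 3.5/10.5/28.5% at 5%. The medullary count is no better, or weaker, in five of these nine cells.

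**How well the expected number can be known.** The whole Database cohort of 750,000 gives 750,000 × 0.0000613 = 46 thyroid cases per year of follow-up, hence 0.9–4.6 medullary cases at s = 2–10%. Its GLP-1 RA users (37,000–74,000 person-years) give 2.27–4.54 thyroid cases and only 0.05–0.45 medullary cases.

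**False triggers with annual looks.** I simulated cumulative counts at years 1 to 5 with no true excess and the same 5% rule at each look. The all-thyroid count alone triggers in about 8–11% of registries, the medullary count alone in about 3–8%, and either of the two in about 10–17%.

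**The case against.** III.9.7 is short and does not rule out a medullary tabulation. A histological subtype beside its parent site is the sort of detail an analysis plan may add, and elsewhere the protocol defines the outcome with the medullary emphasis. The Database Study already aims at medullary results, case details are gathered annually (III.9.3) so a cluster might be noticed, and III.9.5 says power will be defined further. Every magnitude depends on a share the protocol does not supply, and the tables plan for cancer ratios of 1.5 and 2, not ten.

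Much of this stands. All-thyroid cancer is a valid stated outcome that formally addresses the hypotheses as worded, and no printed figure is wrong. The request for a medullary power row is largely answered by the promise to refine power. What remains is that III.9.7 itself lists the outcomes that receive an expected number and a trigger, and that list stops at thyroid cancer. Noticing a cluster is not the same as comparing it with an expected count.

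A reader might infer that the existing rule would usually miss a tenfold medullary excess. That is too strong: its power exceeds 50% in five of the twelve cells above (59%, 51%, 93%, 76% and 99.6%). Nor do the documents show that medullary analysis is excluded, or that the Registry's own variable list names histology. The explicit mention, "the cancer registries (date of diagnosis, cancer site, histology and outcome of cancer", is in the Database Study's section II.9.3. The Registry's route to morphology is through the shared data sources of II.9.4.

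**Conclusion.** The mismatch is in the text: hypotheses that emphasise medullary carcinoma, and a trigger stated for all thyroid cancer. Dilution follows for any share below one; its size depends on the assumed share. The loss is substantial for large excesses when the share is 2–5% and exposure is 5% or less. At a 10% share it is still visible at 1–2% exposure (37% v 69% and 59% v 97%) but has gone, or nearly so, at 5–10% exposure. For a doubling neither count is useful at 5% exposure or below. The power figures treat the expected number as known and use a single five-year test. This is a cheap improvement, not an error that undermines the Registry.

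**What to change.** In III.9.7, and in the synopsis to match:

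- Add a medullary observed/expected count (C73 with medullary morphology) beside the all-thyroid count, with an exact Poisson test and interval.
- Take its expected number from the whole Database Study diabetic cohort, since the GLP-1 RA users alone are expected to yield fewer than one case per year of follow-up. Allow for its uncertainty, for example with the exact conditional comparison of two Poisson counts.
- State that a non-significant all-thyroid ratio is not evidence against a medullary excess.

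A medullary power row in III.9.5, with the assumed share shown, is optional.

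The data are already linked, so the work is one more count. At 1–2% exposure a trigger can rest on one to three cases; with 1% exposure and a 5% share, one case suffices in year 1 and two by year 5. The overall thyroid false-trigger rate over five unadjusted annual looks rises from about 8–11% to 10–17%. That is tolerable because a trigger leads only to possible further investigation, but the section should say so.
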